10. DATA MANAGEMENT

The data management for this NIS will be performed by

The following chapters describe the software employed and measures applied for data security.

NIS data are recorded, processed and stored using the following software tools.

- a. CRF database (Location:)
- b. Patient address database (Location:)
- c. AstraZeneca SAE database (Sapphire, location: AstraZeneca)
- d. Statistical analysis SAS[®] (Location:)

Wherever applicable, current GCP guidelines (Good Clinical practice), actual technical standards and guidelines are observed.

10.1 Employed software

CRF database

For data capturing and data management of this NIS, a web-based validated software (WBDC) will be employed. The software consists of the following modules:

- a) **Administration:** Administration of sites (clinics / office based physicians) by system administrator and project management. Within the individual sites the following system users are defined: Investigator and study nurse. All access rights are administered in a role-based security system.
- b) **Forms / Form validator:** Electronic Case Report Forms (eCRFs) for data capture including online validation of CRFs during data capture, e. g. check on range, plausibility, type mismatch.
In addition to the system based plausibility checks, a formal query process will be implemented to resolve inconsistencies in SAE data.
- c) **Reports:** Dynamic report generator, e.g. reports for investigators on CRF status;
- d) **Database:** Relational database for data management. The data from the relational database will be retrieved using the export engine of _____ and thereafter converted into SAS data sets for further validation and analysis.

The employed technology and technical requirements for data entry on site are as follows:

- a) The used software is completely server-based, i.e. all program processes are executed centrally on a web or database server.
- b) Data are saved exclusively in the central database server. This server is located in the facilities of _____.
- c) For system access, users require a conventional desktop computer with internet access.

A reconciliation of SAE data will be performed every 6 months (after first subject in) to ensure that critical data related to serious adverse events are consistent in the Global safety-database, which is operated by AstraZeneca Drug Safety, and the CRF database. If necessary, discrepancies will be discussed and/or clarified with the participating centres.

Patient address database

For the handling of shipments of patient materials to patients a separate database will be set up, which will contain patient names and addresses. This database will be operated within the facilities of _____. Only authorized personnel will have access to this database.

A relational database will be used for this purpose. The patients address database will be linked through the randomization number with the eCRF database. Links to other databases will not be implemented.

The sponsor will not have access to the data stored in the patient address database.

Statistical analysis (SAS)

For statistical analysis the program SAS[®] will be used.

Data from the CRF database will be transformed into SAS data sets, which will form the basis for the statistical analysis

The date of the final data retrieval from the CRF database will be documented.

10.2 Data security and storage

Data security

For client / server communication via the Internet only encrypted transmissions are applied. State of the art encryption technology is used exclusively. For data transmission in this NIS an encryption level (128-bit) is employed by means of the Secure Socket Layer Algorithm (SSL).

In addition, the server identifies itself to the client workstation by means of a digital server certificate issued by an authorised certification authority. By this, it is ensured that data are sent only to the server of

Data are protected from potential virtual attacks and physical damage.

According to the role of the participating personnel in this NIS (see section 10.1) individual authorisations to the system are granted. Views on data or reports as well as edit or read only rights are controlled with individual passwords. Access authorisation to the CRF databases is granted individually to investigators and program personnel by means of user accounts.

The project management of the CRO has a read-only access to all patient data stored in the CRF database.

Storage

will store all paper documents (facsimile of signed Informed Consent Forms) and all electronically recorded data (i.e. patient address database, CRF database and SAS files) until the completion of this NIS.

At the end of the NIS (final analysis completed) all copies of the signed Informed Consent Forms will be destroyed by . The destruction must be documented and confirmed in written form by .

At the end of the NIS (final analysis completed) all electronically stored data (names and addresses) in the patient address database will be deleted. The deletion must be documented and confirmed in written form by . When the data is deleted from the patient address database all data stored in the CRF database will automatically be anonymised.

After accomplishment of this NIS all electronically captured data during the performance of this NIS, including a copy of the CRF database and the SAS-dataset will be handed over to AstraZeneca and to the principal investigator.

For archiving purposes investigators may receive a hardcopy or a CD-ROM with the data of the enrolled patients at their site.

Provision is made to ensure the readability of electronically stored data over the required storage period.

11. STATISTICAL METHODS AND DETERMINATION OF SAMPLE SIZE

The statistical analysis and reporting of this NIS will be performed by DSH statistical services under the supervision of and in close collaboration with AstraZeneca GmbH.

This section is focused on the first statistical analysis, i.e. after all patients were observed for at least three months. The final statistical analysis (after all patients were observed for 9 months) will be performed in the same way, but using the data in a cumulative way.

11.1 Statistical evaluation – general aspects

A comprehensive Statistical Analysis Plan (SAP) covering details of all methods used to analyze the various parameters will be prepared before database lock of the 3 months data. The SAP will be reviewed, and if needed, updated before this first data base lock.

The disposition of patients with regard to

- the number of patients enrolled,
- the number of patients treated with anastrozole (upfront and following two to three years of tamoxifen treatment),
- the number of patients who discontinued prematurely from the anastrozole therapy within the study period,
- the number of patients who discontinued prematurely from this NIS within the present observational period,
- the number of patients who completed the NIS up to 3, 6, and 9 months after study start,
- the number of patients who are still taking anastrozole up to the time point of the present statistical analysis of this NIS

will be displayed by specialized clinic (including overall). The disposition of the patients in the subsequent final analysis will be displayed in the same way.

Patients without any documented start of an endocrine therapy (e.g. missing information on prescriptions) will be excluded from all statistical analyses, but will be displayed in all data listings.

All treated patients who discontinued prematurely from the anastrozole therapy and/or the NIS (according to the corresponding CRFs) will be listed by clinic; at least the time-point of discontinuation, the main reason for discontinuation and relevant data of exposure to anastrozole will be presented.

The following text refers to more general statistical key-principles based on the statistical analysis data sets, i.e. the intent-to-treat population and the safety population:

Binary, categorical and ordinal parameters will be summarized by means of absolute and percentage numbers (including ‘missing data’ as valid category at Visit 1). Numerical data will be summarized by means of standard statistics (i.e. number of available data, mean, standard deviation, minimum, median, maximum, lower and upper quartile). Wherever useful, the summary statistics will be presented by specialized clinic (including overall) and/or visit.

In addition, adequate figures (e.g. bar charts, Box-Whisker-Plots) may be presented to summarize the results for some parameters also in a graphical way.

All statistical tests will be performed two-sided at a 5% level of significance. However, the p-values of all statistical tests will be interpreted only in a descriptive-exploratory way. Two-sided confidence intervals will be displayed for important variables. Appropriate methods will be used to derive confidence intervals, depending on data nature and distribution. All safety and tolerability data (excluding data obtained on arthralgias) will be presented in a purely descriptive manner. Data from patients, who stopped anastrozole treatment and continued adjuvant endocrine treatment with a different medication will be presented in descriptive way only.

All statistical analyses will be performed using the SAS[®] system.

11.2 Description of outcome variables

The co-primary objective of this NIS will be the evaluation of arthralgia scores and patients’ compliance. Secondary, arthralgia management and related costs (health economic evaluation) as well as the perception of side-effects will be evaluated. Data concerning arthralgia management will be compared to and validated by data obtained by the GWQ.

Compliance:

Compliance is defined by the percentage number of patients being ‘compliant’ to anastrozole therapy, based on the following information collected by the doctor at 0, 3, 6 and 9 months after study start:

1) Question about the daily intake of anastrozole (to be answered by the investigator):

”The patient was instructed to take 1 anastrozole tablet per day. However, it’s still possible that the intake has sometimes been forgotten. How many tablets, according to your impression of the patient, has the patient actually taken during the last year?”

Scoring:	0 – none	0%
	1 – few	[0% ; 20%]
	2 – less than half	[20% ; 40%]
	3 – approximately half	[40% ; 60%]
	4 – more than half	[60% ; 80%]

5 – almost all	[80% ; 100%]
6 – all	100%.

- 2) Question about the daily intake of anastrozole (to be answered by the patient in the patient questionnaire)
”You were instructed to take 1 anastrozole tablet per day. However, it’s still possible that the intake has sometimes been forgotten. How many tablets have you actually taken during the last year?”

Scoring: 0 – none	0%
1 – few	[0% ; 20%]
2 – less than half	[20% ; 40%]
3 – approximately half	[40% ; 60%]
4 – more than half	[60% ; 80%]
5 – almost all	[80% ; 100%]
6 – all	100%.

- 3) A patient will only be defined as being ‘compliant’ when the answer of the doctor **and** the patient score ‘5’ or ‘6’ concerning the question regarding the number of tablets actually taken.

Arthralgias

Arthralgias will be characterized by VAS scores containing 14 items.

Arthralgias will be summarized by incidence, localization, onset, duration, intensity, and relationship to study drug, diagnostics and arthralgia management (e.g. medication, physiotherapy, doctor’s visits, change of life style etc.). Arthralgia characteristics will be particularly assessed using VAS scores (Appendices E and F).

Perception of side-effects

Subjective perception of side-effects will be evaluated using the following scores: GASE-P (Generic Assessment of Side Effects, appendices E and F), SASS (Somatosensory Amplification Scale, appendices E and F), and BMQ (Beliefs about medicines questionnaire, appendices E and F).

Arthralgia therapy and related costs

Arthralgia therapy will be documented in the eCRF and in the patient questionnaire (for further information, see Chapter 8; e.g., newly prescribed medication, doctor’s visits, diagnostics, hospital admissions). Diagnostic and therapeutic measures will be recorded as standardised patterns in the eCRF and in the patient questionnaire and will be correlated with itemised costs for evaluation purposes. Cost evaluations will be feasible on patient and global level.

Each occurrence of arthralgia will be assigned to the corresponding time interval according to 0-3, 3-6, 6-9, 9-12 and 12+ months after the start of anastrozole treatment (i.e. post treatment start).

Validation of data (arthralgia therapy and compliance) by sick fund data

For patients who signed an additional informed consent form (Appendix C, see chapter 7.3), arthralgia therapy as documented by the investigators and the patients will be compared to sick fund data on an individual patient level by a third party who will combine the study and the sick fund datasets on an individual patient level. The third party will combine the sick fund dataset and the study dataset using the patient insurance number which will be sent to on the additional informed consent (Appendix C). The patient insurance number will be immediately deleted after data combination. Statistical evaluation will only be based on pseudonymised data.

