6. PATIENT SELECTION AND PLANNED NUMBER OF PATIENTS

Patients are eligible for inclusion in this NIS if they have taken anastrozole either upfront or following two to three years of tamoxifen treatment (“switch”) for at least three and not more than six months prior to offering an individual participation in this program. Treatment should follow local therapy guidelines and standard practice. Treatment decisions for patients participating in this study including assessments or supportive therapy during follow-up visits will also follow guidelines and remain independent of the program.

The patient population will include postmenopausal women with hormone-receptor positive primary breast cancer scheduled for adjuvant upfront endocrine treatment with anastrozole or following two to three years of tamoxifen treatment (“switch”) according to the current SmPC (Appendix C). Patients will have taken anastrozole for at least three months and not more than six months before the start of the study.

It is planned to enrol and document 3212 patients in this NIS. Further details regarding the objectives and the sample size consideration can be found in Section 3 and 11.5..

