8.1.3 Documentation after 3, 6, and 9 months after study start

The following patient data should be documented after 3, 6, and 9 months after study start or at the time point of treatment discontinuation:

Observation interval	Date of last examination Date of documentation (current date)
Date of observation	
Patient lost to follow-up status	If the patient does not attend follow-up visits, can she be contacted (yes, no – lost to follow-up)
Demographics	Weight (kg)
Occurrence of adverse events	(no, yes) ⇒ AE/SAE-module
Status of breast cancer disease	Loco-regional recurrence / contralateral recurrence / distant metastasis (if yes: date of recurrence / localisation?)
Survival status	(alive, died) ⇒ Survival –module
Continuation of anastrozole therapy (yes, no)	Yes ⇒ Treatment continuation-module No ⇒ Treatment discontinuation module Change of endocrine therapy ⇒ Switch module
Patient continuation of participation in COMPACT	(Yes, no – consent withdrawn, no – died, no – other reasons) ⇒ Consent withdrawal-module
Concomitant medication	No, yes => please specify

The following data should be documented after 3, 6, and 9 months of endocrine therapy or at the time point of treatment discontinuation as indicated and applicable by patient's status:

Treatment continuation – Module (continuation of anastrozole therapy)	
Treatment compliance: doctor's assessment	Estimation of compliance by doctor's judgement: "How many tables have been taken in the observed period?" (none, few, less than half, appr. half, more than half, almost all, all)
Number of medicines / tablets or capsules per day	
Anastrozole prescriptions / sample packages	Number and package size
Was anastrozole intake stopped / taken irregularly?	if yes => reason?
Concomitant medication	No, yes => please specify

Arthralgia – Module (to be filled in in case of arthralgia occurrence during anastrozole therapy)	
Arthralgia questionnaire	
Arthralgia onset during anastrozole therapy (no, yes, unknown – if yes : localisation, swelling, pain intensity; duration, relationship to study drug)
 
Therapy of arthralgias: no, yes – please specify.
 
Assessment of treatment with medication (drug name, dose, package size, duration (start-end))
 
Doctor's visits (including doctor's specification)
 
Diagnostics? if yes => specify
 
Physiotherapy? if yes => specify
 
Adjuvants? if yes => specify
 
Lifestyle changes? if yes => specify

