8.2.2 Documentation at 3, 6 an 9 months after study start

The following data should be documented after 3, 6 and 9 months after study start or at the time point of treatment discontinuation

Demographics	Year of birth
Observation interval	Date of assessment
Demographics	Year of birth

Observation interval	Date of assessment
Medication intake	
Daily intake of drugs/tablets apart from the prescribed anti-cancer agent?
 
Number of drugs and tablets per day? (none, unknown)
 
Self reported medication intake (questions from reference): Do you occasionally forget taking of your medicine ? (yes,

	
no)
 
Are you occasionally neglectful concerning your medicine intake? (yes, no)
 
When you feel better, do you occasionally stop taking your medicine? (yes, no)
 
Sometimes when you feel worse, do you stop taking your medicine? (yes, no)
 
How do you feel about taking your medication?
 
 - never mind - don't like it 
Why don't you like taking your medication?
 
 - difficulties in swallowing tablets - disturbs my daily routine - reminds me of my disease - other 
Compliance to anastrozole: You were supposed to take one tablet anastrozole per day. However, daily medication intake may be forgotten. How many anastrozole tablets did you actually take from the start of anastrozole therapy until today:
 
 - none - few - less than half - almost the half - more than half - almost all - all

Questions on arthralgia occurrence, characteristics and management
	
Did you experience any arthralgias during the past three months? (yes, no)
 
Did the arthralgia intensity change during the past three months? (yes, the intensity decreased; yes, the intensity increased; no)
 
Which medication did you take because of arthralgias?
 
Did you consult any doctor because of arthralgias, and in which field did the doctor specify? (general practitioner, number of times; internist, number of times; orthopedist, number of times; rheumatologist, number of times; pain

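### The co-primary compliance item carries three different recall windows across Sections 3/11.2, the doctor eCRF and the patient questionnaire, and the doctor-and-patient rule combines them without reconciling them

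*Protocol*

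**What the plan says.** Section 11.2 makes compliance part of the main outcome: "The co-primary objective of this NIS will be the evaluation of arthralgia scores and patients’ compliance". The definition, given in the Synopsis, Section 3 and Section 11.2, is "based on the following information collected by the doctor at 0, 3, 6 and 9 months after study start". It has a doctor item, asking how many tablets "has the patient actually taken during the last year", and a patient item, "How many tablets have you actually taken during the last year". The combination rule is strict: "A patient will only be defined as being ‘compliant’ when the answer of the doctor" and that of the patient are both 5 or 6, that is, 80% or more.

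The data-collection sections word the items differently:

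- **Doctor eCRF** (8.1.2 at baseline; continuation and discontinuation modules of 8.1.3): "How many tables have been taken in the observed period" (the spelling is the protocol's). The period is not defined.
- **Patient questionnaire** (8.2.1 at start; 8.2.2 at 3, 6 and 9 months): "How many anastrozole tablets did you actually take from the start of anastrozole therapy until today". The wording is the same at every visit.

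On exposure at entry, Section 6 states: "Patients will have taken anastrozole for at least three months and not more than six months before the start of the study".

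**The concern.** The rule treats the two answers as two views of one quantity. That is true only if both raters look back over the same stretch of time, and the protocol gives three windows without saying which governs.

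If the doctor reports on the last three months and the patient on everything since the first tablet, the composite is neither compliance at a visit nor compliance over the first year. Part of any doctor-patient disagreement would then come from the question and not from intake. If some doctors in the roughly 700 centres read the period one way and some the other, the same intake is classified differently by centre. An analysis plan cannot repair this later, because answers given over the wrong window cannot be converted.

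**Working it through.** **The plan's own figure.** Section 11.5 bases the compliance sample size on 44% against 50% with a continuity-corrected chi-square test, two-sided 5%, 80% power. Recalculation gives 1119 per group (1086 without the correction), as stated. The sample size arithmetic is not in question.

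**Months on drug at each visit.** Entry exposure of 3 to 6 months (Section 6) plus visit month:

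| Visit | Months on drug (T) | Is all intake inside the last 12 months? |
|---|---|---|
| Study start | 3–6 | yes |
| Month 3 | 6–9 | yes |
| Month 6 | 9–12 | yes |
| Month 9 | 12–15 | all but up to 3 months |

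The one-year and since-start windows therefore cover the same tablets up to month 6. At month 9 they differ by at most 15 − 12 = 3 months.

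**What the observed period could mean.** The protocol supports two readings.

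- *Since start of drug:* the second footnote to the flow chart in Section 7.1 speaks of an observation period of 12 (15) months and derives it from the 3 to 6 months of treatment before enrolment. That counts from the first tablet. At baseline there is no earlier visit, so this reading is also natural there.
- *Since the last visit:* the follow-up form in 8.1.3 has an observation-interval row holding the dates of last examination and of documentation.

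**Effect if doctors use the interval reading.** Assume an interval of 3 months, full intake before it, and a fraction r of tablets taken within it. Intake since start is (T − 3 + 3r)/T.

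- T = 9, r = 0.5: (6 + 1.5)/9 = 83.3%, score 5. Over the interval: 50%, score 3. The patient half of the rule is met and the doctor half is not.
- The opposite pattern at T = 9, with half intake for 6 months and then full intake for 3: (3 + 3)/9 = 66.7% since start, score 4; 100% over the interval, score 6. Now the doctor half is met and the patient half is not.

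The lowest r that still reaches 80% since start is (0.8T − (T − 3))/3:

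| T (months) | 6 | 9 | 12 | 15 |
|---|---|---|---|---|
| lowest r | 60% | 40% | 20% | 0% |

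The since-start item thus tolerates more recent non-intake the longer a woman has been on drug. At the month-3 visit (T = 6 to 9) the tolerated recent intake is already 60% to 40%.

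**Can cumulative intake be rebuilt from interval answers?** Take score 5 (80–100%) for 6 months, then score 4 (60–80%) for 3 months:

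- lowest: (6 × 0.8 + 3 × 0.6)/9 = 73.3%
- highest: (6 × 1.0 + 3 × 0.8)/9 = 93.3%

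The range straddles the 80% cut-off, so it cannot be rebuilt reliably.

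**The case against.** The strongest reply is that the windows may coincide in practice. Up to month 6 the one-year and since-start wordings are equivalent, and Section 7.1 allows the observed period to be read as time since start. The objective is compliance within the first year, for which a cumulative answer is defensible. Both the upfront and the switch stratum receive the same forms and have the same entry window, and all p-values are exploratory (Section 11.1). The questionnaires in Appendices E and F are not shown, so the administered wording is unknown. All of this stands. It reduces the likely effect but does not remove the inconsistency, because no section settles the window.

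A reader might infer more than the protocol supports:

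- *That a perfect taker could report only 25–50% at study start* (3/12 to 6/12 of a year's tablets). This needs a 365-day denominator. The item opens with the instruction to take one tablet a day and is answered from none to all, so the natural denominator is tablets due.
- *That a woman who takes few or no tablets in the last three months before month 9 still counts as compliant.* The cases r = 20% at T = 12 and r = 0% at T = 15 give exactly 80%, which lies in both printed bands (60–80% and 80–100%). They also concern only the patient half: a doctor answering for the interval, and aware of the lapse, would score her low. Stopping treatment is documented separately.
- *That compliance per visit cannot be obtained at all.* Under the joint rule an interval answer from the doctor can still register a late fall.

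**Conclusion.** The recall window of a co-primary item is inconsistent within the current text and should be reconciled. Between the one-year and since-start wordings the gap is small: none up to month 6, and at most 3 months at month 9. The material risk is the undefined observed period. Read as the interval since the last visit, it makes the rule combine different quantities, and the same intake can score 5 under one window and 3 under the other (83% against 50% at 9 months on drug).

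That example assumes a 3-month interval and full earlier intake. The interval reading is itself plausible but not established. The size of any shift in the compliance rate cannot be computed, because the protocol gives no distribution of intake over time. It follows that no corrected sample size can be derived and no bias between upfront and switch patients is shown. The comparison between time points named in Section 11.5 is the use most exposed, since a cumulative answer responds slowly to recent change.

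**What to change.** State one explicit recall window for each visit and use identical wording in the Synopsis, Sections 3 and 11.2, the doctor eCRF (8.1.2, 8.1.3) and the patient questionnaire (8.2.1, 8.2.2, Appendices E and F). Remove the observed-period wording or define it.

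If change between time points is to be assessed, ask both raters about the time since the last documentation at 3, 6 and 9 months. Keep the existing since-start item, asked of both raters, for cumulative first-year compliance, and state which item feeds the 5-or-6 rule in which analysis. The since-start item should not be dropped: the 20-point bands do not allow it to be rebuilt, and one missing form would break the chain where Section 11.5 expects 25 to 40% of documentation to be unavailable.

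The cost is one extra or reworded item per form and a matching edit to the definition. It has to be done before the answers are collected.
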